2.3. Objectives

Primary objective

- *To assess the impact of a treatment management call center on the treatment of patients suffering from advanced/metastatic renal cell carcinoma (a/mRCC) treated 1st line with sunitinib.*

Secondary objectives

- *To describe and estimate the proportion of patients who have dose reductions, interruptions or discontinuation of treatment (Sutent®),*
- *To estimate the number of unplanned medical procedures, whether or not related to Sutent® (number of unplanned consultations and hospitalizations),*
- *To assess adherence with treatment (Morisky scale [1, 2]),*
- *To estimate the objective response rate (ORR) according to RECIST criteria v1.1.*
- *To assess patient and doctor satisfaction with the telephone call center,*
- *To describe the process of the telephone calls in terms of the number of calls completed and actions taken by the call center and/or the doctor.*

3. INTERIM ANALYSIS AND FINAL ANALYSIS

No interim analysis is planned.

The **final data analysis** will be performed following the data collection and after freezing the database as approved with Pfizer. After the amendment to the protocol (no. 3.1), it was agreed that the statistical analyses be performed on all patients who were followed up by the telephone “Call Center” platform.

Patients initially included in the “standard follow-up” group will be described for informative purposes from their major characteristics at inclusion and during follow-up.

A final statistical report will describe all of the planned analyses in the SAP and any additional analyses requested. This statistical report will not contain any description or comment about the results.

A study report will be written and submitted to Pfizer. This document will provide a discussed overview of the results of the analyses in order to meet the objectives of the study.

The results of the RENACALL study may be discussed in terms of the results of the SANTORIN study [8].

The reports will be written in French.

4. HYPOTHESES AND DECISION-MAKING RULES

4.1. *Hypotheses*

No statistical tests will be used.

4.2. *Decision-making rules*

Not applicable.

5. ANALYSIS POPULATION

5.1. *Definition of the analysis populations*

Reported population	All patients reported by the investigators in the non-inclusion register and included in the eCRF.
Safety population	Patients treated with Sunitinib.
Full Analysis Set (FAS) Population	All patients included by the investigating doctors who meet the study eligibility criteria and have received at least one dose of Sunitinib

NB: Where applicable, the two subgroups of patients will in all cases be distinguished in the populations: firstly patients included in the “Call Center” arm (**main interest population**) and patients included in the “standard follow-up” arm (**exploratory population**) set up as part of the initial study design (before amendment No. 3 to the protocol).

Table 3: Population in each analysis

Analyses		Populations analyzed	Analysis subgroup*
Description at inclusion		Safety population	Call Center /standard follow-up
Description of follow-up	All data Main data	Safety population Call Center Safety population Standard follow-up	
Primary objective		Safety population	Number of calls made by the call center*
Secondary objectives	Sunitinib treatment details Planned and unplanned medical procedures Adherence to treatment Objective response rate Telephone calls	Safety population Safety population Safety population FAS population Call Center FAS population	Number of calls made by the call center* Number of calls made by the call center* Number of calls made by the call center* Number of calls made by the call center*
	Patient satisfaction Doctor satisfaction	Call Center FAS population who completed a self-administered satisfaction questionnaire Call Center FAS population for which the Doctors have completed a satisfaction questionnaire	Number of calls made by the call center*
Pharmacovigilance		Safety population	

* cf. definition §5.2.

5.2. Analysis subgroup

In the assessment of the treatment call center for patient management, analysis of the objectives may be performed overall and according to the number of calls received (two group classification).

In order to define compliance or non-compliance with the intervention, i.e. in order to define the patient as having actually followed the procedure, the scientific committee will define a **minimum number of 7 successful calls out of the planned 14 calls over 4 cycles, with a required minimum of 6 successful calls during the first two treatment cycles, representing at least 3 calls in each of the first two cycles.**

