The aim of these calls is to support the patients in the management of their treatment by listening to and advising them, implementing preventive measure and taking actions when deemed necessary; the purpose of these calls is to support patients in the management of their sunitinib treatment.

Call frequency is presented in the following figure:

[figure not shown]

Figure 3. Call frequency

The chosen rate is of:

- For the first two cycles, C1 and C2: 5 calls during the first 5 weeks of each cycle (no call during week 6 as the patients are usually seen in consultation),
- For cycles 3 and 4: 2 calls per cycle on weeks 2 and 4.
(decision by the CS not to make calls on weeks 1, 3 and 5).

These calls will be made for patients treated with Sutent®; in the event of termination of treatment during the follow-up period, the call following termination will close the intervention. In the event of cycle start postponement, the first call made shall be postponed to match the expected organisation (cycles 1 and 2: first call during week 1 of the cycle; cycles 3 and 4: first call during week 2 of the cycle).

Call organisation has been defined in collaboration with the concerned healthcare professionals and based on prior experience of therapy management in oncology. It shall be as follows:

- build the patient's trust by covering various aspects of the disease and/or of side effects;
- patient education to avoid serious adverse events (e.g.: dietary advice, sports exercises, etc.);
- guidance and advice when deemed necessary; for example, this may be to:
 - advise the patient to take medicinal products prescribed upstream by his/her physician,
 - guide the patient towards his/her oncologist or general practitioner or other.

The patients will also be able to contact the call centre nurses at any time during the study. A specific module will enable the nurse to record this type of "unscheduled" call.

The platform will also play a coordination role between patients and healthcare professionals, through the following actions:

- Draw up a call report on the e-CRF. This latter shall include the number of successful calls, along with the actions performed by the call centre for each call, such as: no special action, or self-medication, or consultation request to one of the physicians;

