Emphasis shall be placed on the quality of these contacts as they shall promote the involvement and quality of work performed by the participating physicians. Each physician shall, insofar as possible, be monitored by the same research associate, from enrolment to closure of the study.

The research associates shall follow up on incomplete or incoherent data (incoherence, lack of response and omission checks) and shall maintain constant contact with the participating physicians. During the patient selection period and depending on the number of inactive participating physicians (no patient selected), the research associates may be required to make follow-up calls to these latter.

Moreover, a study-specific freephone number shall be set up for the participating physicians, in order to immediately answer any queries they may have throughout the duration of the study.

In terms of traceability, all "incoming" calls via the freephone number and "outgoing" calls (selection call, follow-up call, etc.) will give rise to a written report (date, purpose of the call, steps to take, etc.) and will be entered into a log.

Receipt and input of satisfaction and compliance questionnaires

The compliance and satisfaction questionnaires completed by the patients will be sent directly to Pfizer by means of postage-paid envelopes provided to the participating physicians.

After acknowledging receipt, Pfizer sends them in batches to the CRO in charge of data input, where they are entered in duplicate into the database.

Call management

The nurse in charge of patient follow-up via the "therapy management platform", upon receipt of the contact sheet, will enter the patient's contact details into the CATI system. An call identification number (IDcall) will be assigned to the patient. This database will be secure and accessible via login and password to persons in charge of making the calls from the platform. When recording the patient's file, these data will be encrypted in the database. It will subsequently be impossible to access the complete IDstudy / IDcall / patient details chain.

Calls will then be performed according to intervention procedures (Appendix 8) defined for the patients.

End of study

A patient leaves the study in one of the following cases:

- once all 4 treatment cycles have been completed.
- when the patient stops his/her treatment with sunitinib, for whatever reason.

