8.7.1. Analysis strategy

The main analysis will be performed on the population of patients treated with sunitinib, taking into account all grade 3 or 4 AEs observed. Sensitivity analyses will be conducted:

- **using the "missing=failure" strategy**

Any missing values will be replaced by the value corresponding to failure, i.e. grade 3 or 4 AE. For the main outcome measure analysis, this implies that the patient shall be considered as being in a situation of failure.

- **on a population of treated patients compliant with the procedure**

The choice of a compliance threshold upon intervention must be defined in the detailed statistical analysis plan and before the final analysis is performed. This threshold shall consist in a minimum number of successful calls out of the theoretical total number of 14 calls over the entire follow-up period.

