Name : _____	 antiemetic  antidiarrhoeal  anti-neutropenic  antihypertensive  mouthwashes and local anaesthetics  emollients, moisturising creams  analgesics  anti-gastro-oesophageal reflux agents  bisphosphonates  Other, specify	 Date first taken: _____ / _____ / _____ (DD/MM/YYY)  when necessary	 Ongoing  Stopped, End date _____ / _____ / _____ (DD/MM/YYY)  Not available	 Curative  Preventive  Not available	 Dosage regimen: _____ doses _____ time(s) per day for _____ weeks  Not available	Recommendations: _____  Not available

Instruction: identifying all treatments available to the patient will allow the nurses to adapt the advice and actions to be implemented. The nurses will have received an anonymised copy of the patient's prescriptions from the physician

D.2.3. "Freephone" interview

Instruction: During calls to the freephone number, the nurse can access all of the CATI questionnaire in order to meet the patient's request. Once the patient's request has been dealt with, either the next interview can be conducted, depending on its theoretical date, or an appointment can be made

- What is the reason for your call?
 - Answer, Advice, Action *[Provide the appropriate answer to the question, by reference to the concerned section of the questionnaire]*
- Do you have any other questions or problems you would like to discuss?
 - If yes, *[Go to q1]*
 - If no, *[Go to q3]*

- 3- We had agreed to call you on [date] to go over your health and treatment management in greater detail. Would you like to talk about this now?

- *If yes, [redirection to "Regular" questionnaire]*
- *If no, Could we make an appointment for this interview? [Make an appointment]*

D.3.Compliance and care pathway

If 1st call The rest of the discussion covers the period from the last appointment with your oncologist dated [inclusion date] (*Sutent® initiation consultation*) to the current date.

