8.2.4. Analysis of the primary end point

Analysis population: Safety population

The proportion of patients with at least one grade 3 or 4 AE whether or not related to sunitinib, will be estimated.

All of the grades 3 or 4 AEs defined by the 'Common Terminology Criteria for Adverse Events' (CTCAE v4.03 of June 2010), whether or not related to sunitinib, will be included when these occur during the study follow-up period (up to the end of the 4th treatment cycle or until the treatment is stopped if it is discontinued in the 1st, 2nd or 3rd cycle). All of the AEs will be included whether these are declared by the doctor or by the nurse.

The analyses will be performed both on an overall basis and according to the number of calls made by the call center.

Sensitivity analyses:

The sensitivity analyses will be performed:

- Sensitivity to duration of patient treatment: the results will also be expressed as standardized grade 3 or 4 AE rates developed by the patient and reported over the 6 months of treatment. These rates will be defined by each patient as the number of events which occurred/number of treatment months with sunitinib/ 6).

Secondary analysis:

- **The incidence of the main grade 3 or 4 AEs, whether or not related to sunitinib,** will also be presented in these patients according to the MedDRA SOC (System Organ Class) and PT (Preferred Term) classification. Only categories involving at least 2% of patients will be presented.

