8.2.5. Analysis of the secondary end points

8.2.5.1. Sunitinib treatment

Populations analyzed: Safety population

End points:

The analysis of sunitinib treatment methods will be carried out using the following indicators:

▪ **Description of dose reductions**

- Proportion of patients with at least one dose reduction during the period of sunitinib treatment;
- Reasons for the dose reduction: Proportion of patients involved on at least one occasion for each of the reasons for a dose reduction;
- Average dose reduction.

▪ **Description of interruptions to treatment**

- Proportion of patients who interrupted sunitinib treatment temporarily during treatment (including declared temporary interruptions and cases in which the start of the later cycle was deferred);
- Mean duration (in days) of interruptions to treatment by patient (declared duration of interruption or number of days delay identified for the start of the subsequent cycle);
- Reason for interruptions: Proportion of patients involved on at least one occasion for each of the reasons for interruption of treatment (AE, radiotherapy, surgery or other).

▪ **Description of permanent treatment discontinuations**

- Proportion of patients who discontinued sunitinib permanently;
- Reason for discontinuation: proportion of patients involved on at least one occasion for each of the reasons for discontinuation;
- Duration of treatment with sunitinib: time between starting sunitinib and the notified date to discontinue it or the date of the last consultation if sunitinib treatment was not stopped;
- Number of treatment cycles before discontinuation.

The analysis will be performed both on an overall basis and according to the number of calls made by the call center.

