9.4. Analysis of the primary end point

Table 30: Development of AEs during the follow-up period (safety population)

		Number of calls received < xx (N=xxx)	Number of calls received ≥ xx (N=xxx)	Call center (N=xxx)
At least 1 grade 3 or 4 AE whether or not related to Sunitinib	Yes	xx (xx%) [xx; xx]	xx (xx%) [xx; xx]	xx (xx%) [xx; xx]
	No	xx (xx%)	xx (xx%)	xx (xx%)
Number of grade 3 or grade 4 AEs, whether or not related to Sunitinib per patient	Number analyzed	xxx	xxx	xxx
	Mean (±SD)	xx (± xx)	xx (± xx)	xx (± xx)
	Median	xx	xx	xx
	Min-Max	xx - xx	xx - xx	xx - xx
Standardized grade 3 or 4 AEs, whether or not related to Sunitinib per patient, reported over the 6 months of treatment	Number analyzed	xxx	xxx	xxx
	Mean (±SD)	xx (± xx)	xx (± xx)	xx (± xx)
	Median	xx	xx	xx
	Min-Max	xx - xx	xx - xx	xx - xx

Table 31: Description of grade 3 and 4 AEs related or unrelated to sunitinib recorded during the follow-up period (safety population)

		Number of calls received < xx (N=xxx)	Number of calls received ≥ xx (N=xxx)	Call center (N=xxx)
Type of grade 3 or 4 AEs, whether or not related to Sunitinib (SOC – MedDRA category)*	xxxx	xx (xx%)	xx (xx%)	xx (xx%)
	xxxx	xx (xx%)	xx (xx%)	xx (xx%)
	xxxx	xx (xx%)	xx (xx%)	xx (xx%)
Type of grade 3 or 4 AEs, whether or not related to Sunitinib (PT – MedDRA category)*	xxxx	xx (xx%)	xx (xx%)	xx (xx%)
	xxxx	xx (xx%)	xx (xx%)	xx (xx%)
	xxxx	xx (xx%)	xx (xx%)	xx (xx%)

* Categories involving at least 2% of patients

These tables are described for patients under standard follow-up also for exploratory purposes.

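### The SAP 5.2 call split puts patients who stop sunitinib early in the low-call column even if they answered every call, so Table 36 compares stopping between groups partly defined by stopping

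*SAP*

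**What the plan says.** Protocol 8.7.1 asks for a sensitivity analysis in patients compliant with the procedure, with a threshold set as a "minimum number of successful calls out of the theoretical total number of 14 calls over the entire follow-up period". SAP 5.2 supplies it: a "minimum number of 7 successful calls out of the planned 14 calls over 4 cycles, with a required minimum of 6 successful calls" in the first two cycles, at least 3 in each. That section says analyses by call group may be done. SAP 8.2.4 (primary endpoint) and 8.2.5.1 (sunitinib treatment) are firmer: "The analysis will be performed both on an overall basis and according to the number of calls made by the call center" is the wording in 8.2.5.1. The two call columns appear in Tables 30, 31, 33, 35, 36 and 44.

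Whether a call takes place depends on treatment. Protocol 8.2 says that "in the event of termination of treatment during the follow-up period, the call following termination will close the intervention", and that a patient leaves the study "when the patient stops his/her treatment with sunitinib, for whatever reason". Under SAP 8.2.4, grade 3 or 4 events count only "until the treatment is stopped if it is discontinued in the 1st, 2nd or 3rd cycle".

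**The concern.** The threshold is a count against a fixed 14 calls, with no allowance for calls that were never due because the patient had stopped. An early stopper who answered everything is classed as not having followed the procedure.

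Table 36 shows the fault most clearly: its outcomes are stopping, number of cycles before stopping and time on treatment, and the columns depend on all three. The low-call column will show more stopping and shorter treatment even if the platform does nothing. SAP 5.2 presents the split as part of assessing the call center, and there is no longer a randomised comparator, so a reader could take the difference for a platform effect. SAP section 3 says the statistical report will carry no comment on results, so in that report the table would stand without a caveat unless the SAP provides one.

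**Working it through.** **1. The plan's own figure.** Protocol 8.2 schedules 5 calls in each of cycles 1 and 2 and 2 in each of cycles 3 and 4: 5 + 5 + 2 + 2 = 14, which reproduces.

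**2. Most calls a patient can have, answering every one.** The rule is total ≥ 7, cycle 1 ≥ 3 and cycle 2 ≥ 3.

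| Stops just after | Without closing call: total (C1/C2) | Rule met | With closing call: total (C1/C2) | Rule met |
|---|---|---|---|---|
| Week 5 or 6 (cycle 1) | 5 (5/0) | no | 6 (5/1) | no |
| Week 7 (first cycle 2 call) | 6 (5/1) | no | 7 (5/2) | no |
| Week 8 (second cycle 2 call) | 7 (5/2) | no | 8 (5/3) | yes |
| Week 9 (third cycle 2 call) | 8 (5/3) | yes | 9 (5/4) | yes |

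Low-call status is therefore forced for stops before about week 8 to 9. The boundary is approximate: calls shift when a cycle is postponed, and during a freephone call "either the next interview can be conducted, depending on its theoretical date" (Appendix 7, D.2.3). The SAP does not say whether the closing call counts. If the Table 36 row for cycles before discontinuation means cycles started (it has no zero category), its entry for 1 cycle must be empty in the compliant column.

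**3. Column labels.** A single cut-off on number of calls cannot express the rule. A patient with 5 + 2 + 2 + 2 = 11 calls fails (only 2 in cycle 2), while 3 + 3 + 1 = 7 passes.

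**4. Size, with calls having no effect.** The documents give no stop rate, call-success rate, event timing or share of events leading to a stop. Protocol 6.1.2 quotes 58% with a grade 3 or 4 event in a French real-life study, without a time window. The assumptions were:

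- 58% event risk over 24 weeks before truncation by stopping (50 to 56% observed after it).
- 0, 15, 30, 50 or 70% of first grade 3 or 4 events leading to a stop.
- 10% or 29% other stops by week 24.
- Call success of 70, 80 or 90%.
- Three hazard shapes: both constant, events front-loaded, both front-loaded.
- Calls at weeks 1–5, 7–11, 14, 16, 20 and 22 while on drug, plus a closing call at the next slot.

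That is 5 × 2 × 3 × 3 = 90 scenarios, with 200,000 patients each. Gaps are low-call minus compliant, in percentage points:

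| Call success | Stopped sunitinib | Primary endpoint |
|---|---|---|
| 70% | +11 to +49 | −15 to +28 |
| 80% | +24 to +61 | −24 to +38 |
| 90% | +56 to +81 | −37 to +46 |

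Middle case (30% of events leading to a stop, 29% other stops, 80% call success, constant hazards): stopped 77% vs 28%; mean time on drug 9.8 vs 21.7 weeks; primary endpoint 48% vs 51%. Across the three hazard shapes the stopping gap is +49.2, +53.7 and +61.0, and the primary gap −3.4, +6.5 and −2.1. Recalibrating so that the observed event proportion is 58% gives stopping gaps of +50.3, +54.3 and +61.7 and primary gaps of −4.7, +5.2 and −4.2.

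In every scenario no compliant patient had stopped by week 6; the shortest time on drug in that group was 8.0 weeks. Patients who failed the rule although every call was answered numbered 3 to 38 per 100 (17 to 25 in the middle case).

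**5. A simpler model agrees.** Take a constant weekly stop hazard h = 1 − (1 − F)^(1/24), unrelated to calls, with F = 30% stopping by week 24. Stoppers in the low-call and compliant columns are 100% vs about 22% if every call is answered, 63–65% vs 20–22% at 80% call success, and 46–47% vs 19–21% at 70%.

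**6. After separating stops before the end of cycle 2 (week 12).** At 80% call success the remaining gaps are −0.6 to +1.1 (stopping) and −0.6 to +0.6 (primary). At 70% they are −0.1 to +1.0 and −0.3 to +0.8. At 90% they are within 1.9 and 2.4, mostly simulation noise because only 1–2% of patients remain in the low-call group.

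**The case against.** The strongest reply is that little rests on this split. No tests are planned (SAP 4.1), the principal analysis uses all Call Center patients whatever their calls (SAP 8.1.2), and an overall column is shown. Table 36 prints reasons, cycles and duration by column, so an attentive reader could see the early stopping. All of that stands and limits the consequence, but it does not make the column contrast interpretable.

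SAP 8.2.4 also plans event rates standardised to six months of treatment, and Table 30 shows them by call group. That addresses time on drug for the primary endpoint. It was not simulated here, so the primary-endpoint ranges above apply to the crude proportion only. It does nothing for Table 36.

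The fixed denominator comes from the protocol, and the rule can be read as intervention received. But the protocol asked for one compliant population as a sensitivity analysis, not a side-by-side contrast with everyone else.

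Three smaller points have some force. If the cycles row means completed cycles, a patient who stops in cycle 2 after three calls counts as 1 and can be compliant. The cut-off in the table headings is a placeholder, and Table 3 refers back to 5.2. The 70 to 90% range of call success is a choice: at 50% and 60% the stopping gap is smaller (+6 to +35 and +7 to +40), though still positive. The simulation also ignores cycle postponement and any link between health and answering calls.

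**Conclusion.** The concern holds. That early stoppers are forced into the low-call column follows from the call schedule and the 5.2 rule alone. The direction of the Table 36 artefact was the same in every scenario run; its size depends on assumed stop and call-success rates. For the crude primary endpoint the artefact can take either sign, and the documents do not allow its size to be fixed. This is a flaw in a planned descriptive split that should be corrected; the main estimate is not affected.

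**What to change.** 1. In every table split by calls, give patients who stopped sunitinib before the end of cycle 2 their own column. Apply the 5.2 rule only to the rest, for whom all ten cycle 1 and 2 calls were due. Footnote how many early stoppers had met the rule, so that the protocol 8.7.1 compliant population can still be rebuilt (about 1 to 7 per 100 at 80% call success).
2. Label the columns by the full 5.2 rule, and say whether the closing call counts.
3. State that the split is descriptive and is not evidence of platform impact.

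The cost is SAP wording, one derived variable and new column labels; no new data are needed. Because this departs from the two-group classification in SAP 5.2, the scientific committee should agree it. The early-stopper column would hold about 5 to 45 per 100 patients (25 to 31 in the middle case) and by construction shows 100% stopping in Table 36.

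The main drawback is a small remaining low-call group: about 17 to 29 per 100 at 70% call success, 6 to 11 at 80% and 1 to 2 at 90%. With 6 to 11 patients the 95% half-width at p = 50% is 1.96 × √(0.25/n), about 40 to 30 points, so the sufficient-numbers condition in SAP 8.1.2 may suppress the column. Confounding by health or reachability would remain. Showing Table 36 overall only is a simpler alternative for that table, but it leaves the other split tables unchanged.
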